8.1.6.1 DTSQs

8.1.6.2 DTSQc

The Diabetes Treatment Satisfaction Questionnaire Status Version (DTSQs) will be used to evaluate patient satisfaction with treatment and patient perception of blood glucose control over a several week period (16). The DTSQs is a validated questionnaire comprised of 8 questions which are answered on a Likert scale from 0 to 6. Responses to 6 of the items will be summed to produce a Total Treatment Satisfaction score ranging from 0 (no satisfaction) to 36 (high satisfaction with treatment). The 2 items of 'perceived frequency of 'hyperglycemia' (Item 2) and 'perceived frequency of hypoglycemia' (Item 3) are scored separately ranging from 0 (none of the time) to 6 (most of the time). The DTSQs will be completed by the patients at baseline and Week 12. Mean differences in scores from baseline and between groups will be evaluated to understand the impact of treatment on patient satisfaction.

The DTSQs is available in appendix 5 (Section 10.5).

The Diabetes Treatment Satisfaction Questionnaire Change Version (DTSQc) was developed from the original DTSQ to evaluate the change in treatment satisfaction at a specific time point. The DTSQc instructions and response options differ from those of the DTSQs to produce measures of relative change in satisfaction rather than measures of absolute satisfaction.

It will be used to measure patient perception of change in treatment satisfaction at 12 weeks. Scores for DTSQc treatment satisfaction items range from -3 to +3, and the sum of the treatment satisfaction score range from -18 to +18. Positive scores are indicative of improvement in treatment satisfaction, whereas negative scores are indicative of deterioration in treatment satisfaction since start of the study. Perceived frequency of hyperglycemia and hypoglycemia

scores range from -3 to +3, with negative scores indicating fewer problems with blood glucose levels and positive scores indicating more problems than before. DTSQc will be completed by the patients at 12 weeks after the DTSQs (status version). To control for baseline scores, DTSQs will be used as a measure of treatment satisfaction at baseline.

The DTSQc is available in appendix 5 (Section 10.5).

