1.5 MODIFICATIONS TO THE STATISTICAL SECTION OF THE PROTOCOL

Following the updated version of 'Clinical Targets for Continuous Glucose Monitoring Data Interpretation: Recommendations From the International Consensus on Time in Range' in 2019 (1), some exploratory endpoints were added related CGM

- Mean glucose
- Glucose Management Indicator (GMI) (2) as defined by GMI (%) = 3.31+0.02392*(mean • glucose in mg/dL)
- Percent time and mean hours per day in the glucose range of \geq 54 to <70 mg/dL (\geq 3.0 to • <3.9 mmol/L) (on all-time and during the night [00:00 to 05:59]),
- Percent time and mean hours per day in the glucose range of >180 to \leq 250 mg/dL (>10 to \leq 13.9 mmol/L) (on all-time and during the night [00:00 to 05:59]),

Following a misprint in 'International Consensus on Use of Continuous Glucose Monitoring' in 2017 (3), corrected in CGM consensus in 2019, an update of threshold for glucose within-day CV was done: \leq 36 % instead of < 36%

For consistency between CGM endpoints and safety endpoints, the following endpoints related to hypoglycemia were added:

• Hypoglycemia (symptomatic or asymptomatic) documented by a measured plasma glucose concentration of <3.9 mmol/L (< 70 mg/dL) and ≥3.0 mmol/L (≥54 mg/dL), on all-time and during the night [00:00 to 05:59]

As per FDA & EMA guidelines provided during COVID-19 pandemic situation, several considerations (new population set call "Population without trial impact (disruption) due to COVID-19" and sensitivity analyses) were considered during the Statistical Analysis Plan (SAP) finalization.

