2.1.3.3 Tertiary/exploratory efficacy endpoint(s)

To address the tertiary objective of exploring the glycemic control and variability parameters in each treatment group at Week 12 using CGM, the following endpoints will be assessed:

- Mean hours per day in the glucose range of \geq 70 to \leq 180 mg/dL (\geq 3.9 to \leq 10 mmol/L),
- Percent time and mean hours per day in the glucose range of \geq 70 to \leq 140 mg/dL (\geq 3.9 to \leq 7.8 mmol/L) (on all-time and during the night [00:00 to 05:59]),
- Nocturnal [00:00 to 05:59] percent time in glucose range of \geq 70 to \leq 180 mg/dL (\geq 3.9 to \leq 10 mmol/L),
- Day time [06:00 to 23:59] percent time in glucose range of ≥70 to ≤180 mg/dL (≥3.9 to ≤10 mmol/L),
- Percent time and mean hours per day with glucose <54 mg/dL (<3.0 mmol/L) (on all time and during the night [00:00 to 5:59]),

- Percent time with glucose <70 mg/dL (<3.9 mmol/L) within the 12 hours after basal insulin injection,
- Percent time and mean hours per day with glucose >250 mg/dL (>13.9 mmol/L),
- Mean glucose profile over a 24-hour period,
- 24-hour Glucose Area Under the Curve (AUC mg/dL*minutes), derived using the trapezoidal rule. The derivation will be adjusted to be an hourly average (Section 2.5.2.1),
- Mean glucose,
- GMI,
- Percent time and mean hours per day in the glucose range of ≥54 to <70 mg/dL (≥3.0 to <3.9 mmol/L) (on all-time and during the night [00:00 to 05:59]),
- Percent time and mean hours per day in the glucose range of >180 to $\leq 250 \text{ mg/dL}$ (>10 to $\leq 13.9 \text{ mmol/L}$) (on all-time and during the night [00:00 to 05:59]).

Other tertiary/exploratory endpoints than those related to CGM:

- Daily insulin doses (total daily insulin, basal insulin, mealtime insulin, ratio of basal to mealtime insulin dose) in units and U/kg body weight at each visit. Change at Week 8 and Week 12 from baseline will be derived.
- Change from baseline to Week 12 in patient-reported outcomes (treatment satisfaction, sleep quality and quantity, and productivity) (for detail on PROs, see Section 2.1.7).
- 7-point SMPG profiles (pre-prandial and 2-hour postprandial plasma glucose at breakfast, lunch, dinner, and bedtime) at Week 12 and change in 7-point SMPG profiles from baseline to Week 12.

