2.4.7 Analyses of quality of life/health economics variables

The analyses will be done on ITT population.

For DTSQs, MOS-Sleep, and WPAI, a descriptive summary of each score (see Section 2.1.7) will be done at baseline and at Week 12.

Change in DTSQs, MOS-Sleep, and WPAI scores from baseline to Week 12 will be analyzed using an ANCOVA model including the fixed categorical effects of treatment group (Toujeo, Tresiba), and the randomization stratum of HbA1c at screening (< 8.0%, $\geq 8.0\%$), as well as, the continuous fixed covariate of baseline score.

LS means and the corresponding SEs and 95% confidence interval by treatment for the change from baseline will be presented for descriptive purposes.

The DTSQc score will be analyzed using descriptive statistics at Week 12.

The DTSQc scores at Week 12 will be analyzed using an ANCOVA model including the fixed categorical effects of treatment group (Toujeo, Tresiba), DTSQs score at baseline, and the randomization stratum of HbA1c at screening (< 8.0%, $\geq 8.0\%$).

LS means differences in scores between treatment groups and its SEs and their corresponding 95% confidence interval of will also be evaluated.

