7 LIST OF APPENDICES

Appendix A: Summary of statistical analyses

Appendix B: Questionnaires (PROs)

APPENDIX A: SUMMARY OF STATISTICAL ANALYSES

EFFICACY ANALYSIS

Endpoint	Analysis population	Primary analysis	Supportive analysis	Subgroup analysis	Other analyses
Primary endpoint					
Percent of time in glucose range of ≥70 to ≤180 mg/dL (≥3.9 to ≤10 mmol/L) using continuous glucose monitoring (CGM) at Week 12	ITT, PP, ITT COVID 19 free	For ITT population: ANCOVA with fixed categorical effects Trt and randomization stratum HbA1c and continuous fixed covariate of baseline percent in range value with multiple imputation of missing data Non inferiority with a relative non- inferiority margin of 10 % is the primary analysis	1st Sensitivity analyses: same modeling (ANCOVA) with MI on PP population 2nd Sensitivity analyses same modeling (ANCOVA) with multiple imputation of missing data being imputed in conjunction with MNAR assumption from ITT population. 3rd sensitivity analyses: same	Yes, subgroup by screening and baseline factors such as duration of diabetes, Gender, Randomization strata, BMI.	In addition to the non-inferiority testing that is the primary analysis, and only if non-inferiority of Toujeo in comparison to Tresiba on the percent time in the range of 70-180 mg/dL is demonstrated and if non-inferiority of Toujeo versus Tresiba on the glucose total CV is demonstrated, superiority of Toujeo over Tresiba on the percent time in the range of 70-180 mg/dL will be tested
			modeling (ANCOVA) with MI on Population without trial impact		
			(disruption) due to COVID-19		

Statistical Analysis Plan HOE901-U300-LPS14947		01-Jul Versio)1-Jul-2021 /ersion number: 1		
Endpoint	Analysis population	Primary analysis	Supportive analysis	Subgroup analysis	Other analyses
Secondary endpoints					
Glucose total CV using CGM at Week 12 (Main secondary endpoint)	ITT	ANCOVA model to perform the analysis includes the fixed categorical effects of treatment group (Toujeo, Tresiba),and randomization stratum of screening HbA1c (<8.0%versus ≥8.0%), as well as, the continuous fixed covariate of baseline value for the corresponding endpoint As this is the main secondary endpoint: Multiple imputation (as for primary endpoint) and non-inferiority with a relative non-inferiority margin of 10 % tested in case of non-inferiority demonstrated for primary analysis of primary endpoint	No	No	No

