Nocturnal percent time in CGM glucose range of ≥70 to ≤180 mg/dL (≥3.9 to ≤10 mmol/L) at Week 12, obtained using CGM	ITT	Descriptive summary statistics by treatment group	No	No	No
Percent time and mean hours per day with CGM glucose: <54 mg/dL, (for all time and during the night [00:00 to 05:59])	ITT	Descriptive summary statistics by treatment group	No	No	No
Percent time with CGM glucose <70 mg/dL within the 12 hours after basal insulin injection	ITT	Descriptive summary statistics by treatment group	No	No	No
Percent time and mean hours per day with CGM glucose >250 mg/dL	ITT	Descriptive summary statistics by treatment group	No	No	No
Mean CGM glucose profile over 24-hour period	ITT	Graphic presentation	No	No	No

Statistical Analysis Plan HOE901-U300-LPS14947

01-Jul-2021 Version number: 1

Endpoint	Analysis population	Primary analysis	Supportive analysis	Subgroup analysis	Other analyses
24h-AUC of CGM glucose values	ITT	Descriptive summary statistics by treatment group	No	No	No
Mean glucose	ITT	Descriptive summary statistics by treatment group	No	No	No
GMI	ITT	Descriptive summary statistics by treatment group	No	No	No
Percent time and mean hours per day in the CGM glucose range of ≥54 to <70 mg/dL (for all-time and during the night [00:00 to 05:59]),	ITT	Descriptive summary statistics by treatment group	No	No	No
Percent time and mean hours per day in the glucose range of ≥180 to <250 mg/dL (on all-time and during the night [00:00 to 05:59]),	ITT	Descriptive summary statistics by treatment group	No	No	No
Daily insulin doses (total daily insulin, total basal insulin, total mealtime insulin, ratio of basal to mealtime insulin dose) in units and U/kg body weight	Safety	Descriptive summary statistics (including change from baseline to Week 12) by treatment group	No	No	No
PROs endpoints					
DTSQs	ITT	Change in DTSQs scores from baseline to Week 12 will be analyzed using an analysis of covariance (ANCOVA) model including the fixed categorical effects of treatment group (Toujeo, Tresiba), and the	No	No	No

01-Jul-2021 Version number: 1

Endpoint	Analysis population	Primary analysis	Supportive analysis	Subgroup analysis	Other analyses
		randomization stratum of HbA1c at screening (< 8.0% , $\geq 8.0\%$), as well as, the continuous fixed covariate of baseline score.			
		LS means and its corresponding 95% confidence interval by treatment for the change from baseline will be presented for descriptive purposes			

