DTSQc	ITT	The DTSQc scores at Week 12 will be analyzed using an analysis of covariance (ANCOVA) model including the fixed categorical effects of treatment group (Toujeo, Tresiba),and the randomization stratum of HbA1c at screening (<8.0%, \geq 8.0%).	No	No	No
		LS means and its corresponding 95% confidence interval by treatment for the change from baseline will be presented for descriptive purposes			
MOS Sleep	ITT	Change in MOS-Sleep from baseline to Week 12 will be analyzed using an analysis of covariance (ANCOVA) model including the fixed categorical effects of treatment group (Toujeo, Tresiba), and the randomization stratum of HbA1c at screening (<8.0%, ≥8.0%), as well as, the continuous fixed covariate of baseline score.	No	No	No
		LS means and its corresponding 95% confidence interval by treatment for the change from baseline will be presented for descriptive purposes			

01-Jul-2021 Version number: 1

Endpoint	Analysis population	Primary analysis	Supportive analysis	Subgroup analysis	Other analyses	
WPAI	ITT	Change in WPAI scores from baseline to Week 12 will be analyzed using an analysis of covariance (ANCOVA) model including the fixed categorical effects of treatment group (Toujeo, Tresiba), and the randomization stratum of HbA1c at screening (<8.0%, ≥8.0%), as well as, the continuous fixed covariate of baseline score LS means and its corresponding 95% confidence interval by treatment for the change from baseline will be presented for descriptive purposes	No	No	No	

ANCOVA = analysis of covariance; ITT = intent-to-treat; PP = per-protocol

SAFETY ANALYSES

Endpoint	Analysis population	Primary analysis	Supportive analysis	Subgroup analysis	Other analyses
Number of patients with adverse events	Safety	Summary by treatment group using number and % of patients experiencing at least one adverse event, focusing on TEAE	No	No	No
Number of patients with at least one hypoglycemic event from baseline to Week 12	Safety	Summary by treatment group using number and % of patients experiencing at least one hypoglycemic event will be presented for any hypoglycemia and for each type of hypoglycemia, overall and according to time of occurrence (nocturnal [ie, 00:00 to 05:59], any time of day and daytime [ie, 06:00 to	No	No	No

Statistical Analysis Plan
HOE901-U300-LPS14947

Endpoint	Analysis population	Primary analysis	Supportive analysis	Subgroup analysis	Other analyses	
		23:59] during the 12-week on treatment period				

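### Two rows of SAP Appendix A contradict the SAP body: the DTSQc model omits baseline DTSQs, and the 180–250 mg/dL glucose band has its limits the wrong way round

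*SAP*

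**What the plan says.** **DTSQc model.** Protocol 8.1.6.2 states the intent: "To control for baseline scores, DTSQs will be used as a measure of treatment satisfaction at baseline". SAP 2.4.7 carries it through with an ANCOVA whose terms, after treatment, are "DTSQs score at baseline, and the randomization stratum of HbA1c at screening". It then asks for LS mean differences between the groups. The DTSQc row of SAP Appendix A reads "The DTSQc scores at Week 12 will be analyzed using an analysis of covariance (ANCOVA) model including the fixed categorical effects of treatment group" and continues with "Toujeo, Tresiba),and the randomization stratum of HbA1c at screening". No baseline score appears. The row then says that LS means will be presented for the change from baseline. The DTSQs, MOS Sleep and WPAI rows of the same table all keep the baseline score as a continuous covariate.

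**Glucose band.** SAP 1.5 adds an exploratory endpoint, "Percent time and mean hours per day in the glucose range of >180 to" an upper limit of ≤250 mg/dL, and SAP 2.1.3.3 repeats those limits. Appendix A lists it as "Percent time and mean hours per day in the glucose range of ≥180 to <250 mg/dL". The primary endpoint in the same table is "Percent of time in glucose range of ≥70 to ≤180 mg/dL (≥3.9 to ≤10 mmol/L) using continuous glucose monitoring (CGM) at Week 12", so it includes 180. The top band is >250 mg/dL in both places, so it excludes 250.

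**The concern.** Each of these two analyses has two specifications in the current SAP (version 1, 01-Jul-2021), and they cannot both be followed. Appendix A is the summary table of analyses, so it is a natural source for table shells and programs.

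For the DTSQc, an analyst who followed Appendix A would discard a baseline adjustment that the protocol intends and for which the data are collected. The trial is open-label, so it should also be clear beforehand which of the two models was planned for a satisfaction score.

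For the glucose band, the Appendix A limits no longer fit the bands on either side. The reported time at 180–250 mg/dL would overlap time in range and leave a gap below the top band.

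**Working it through.** The plan states no figure for either item, so there is none to reproduce. The check is a comparison of the texts, a band count, and one standard formula.

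**1. DTSQc model, side by side**

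| Source | Terms besides treatment | Quantity reported |
|---|---|---|
| Protocol 8.1.6.2 | baseline DTSQs named as the control for baseline | not specified |
| SAP 2.4.7 | baseline DTSQs, HbA1c stratum | between-group LS mean differences at Week 12 |
| SAP Appendix A | HbA1c stratum | LS means by treatment for the change from baseline |

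The DTSQc is completed once, at Week 12 (Protocol 1.3; SAP 2.1.7.2). There is no baseline DTSQc from which to compute a change.

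**2. Cost of omitting the covariate**

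Let r be the correlation between DTSQc and baseline DTSQs within arm and stratum. Adjustment reduces the residual variance from σ² to σ²(1 − r²). Omitting the covariate therefore multiplies the variance of the treatment difference by about 1/(1 − r²), ignoring the single degree of freedom. The documents give no value for r, so the range is an assumption.

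| Absolute r (assumed) | 1/(1 − r²) | Variance increase | CI width increase (square root) |
|---|---|---|---|
| 0.3 | 1/0.91 = 1.099 | about 10% | about 5% |
| 0.4 | 1/0.84 = 1.190 | about 19% | about 9% |
| 0.5 | 1/0.75 = 1.333 | about 33% | about 15% |

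Randomization keeps the expected difference the same with or without the covariate. The loss is in precision only.

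**3. Band count**

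Every whole-number glucose value from 39 to 401 mg/dL was assigned to five bands: <54, 54 to <70, 70 to 180 inclusive, the 180–250 band, and >250.

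- Body limits (>180 to ≤250): every value falls in exactly one band.
- Appendix A limits (≥180 to <250): 180 falls in two bands (time in range and this one), and 250 falls in none.

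Let p180 and p250 be the shares of readings exactly equal to 180 and 250 mg/dL. Under the Appendix A limits:

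- 180–250 band plus >250 band = share >180 + p180 − p250, so the two upper bands do not reproduce the secondary endpoint >180 mg/dL (SAP 2.1.3.2);
- all five bands together = 100% + p180 − p250.

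The documents give no glucose distribution. As one illustration, assume whole-number readings from a lognormal distribution with mean 181 mg/dL and CV 38%. Then p180 is about 0.59% and p250 about 0.25%, so the total is 100 + 0.59 − 0.25, or about 100.3%.

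**The case against.** The best defence is that the SAP already points to the right text. SAP 2.4.4.4 refers to Section 2.1.3.3 for the tertiary variables and to Section 2.4.7 for the PRO analyses, and Appendix A is only a summary. This makes misuse less likely. It does not remove the conflict, because the SAP has no clause saying that the body prevails over the appendix.

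The wording about change can also be defended in part. The DTSQc measures perceived change since the start of the study, so the Appendix A phrase is poor rather than meaningless. It still does not describe the between-group comparison in SAP 2.4.7, and it matches the neighbouring rows closely enough to suggest carry-over.

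The effects are small. Both endpoints are exploratory, their results are descriptive, and nothing in the documents requires the bands to total 100%. All of this stands. A PDF-reading error is an unlikely explanation for the band, since both signs are reversed while those in adjacent rows are intact.

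A reader might infer more than the documents support:

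- **That the omitted baseline score was there to handle a ceiling effect.** Protocol 8.1.6.2 speaks only of controlling for baseline scores. Ceiling effects appear only in the title of a cited reference.
- **That SAP 2.4.7 turns the 0–36 DTSQs score into as many as 37 classes,** because it stands in a list opened by categorical effects. The same sentence calls the model an ANCOVA, and the section names a continuous covariate for the other PRO models. This is loose syntax that deserves a clarifying word, not a planned categorical analysis.

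**Conclusion.** The point holds as an internal inconsistency in two Appendix A rows, and it is minor. The DTSQc row contradicts both SAP 2.4.7 and the protocol. If followed, it would give an unbiased comparison with variance about 10% to 33% higher, provided that the correlation with baseline DTSQs lies between 0.3 and 0.5 in absolute value. The band row contradicts SAP 1.5 and 2.1.3.3. That one value is counted twice and another not at all follows from the stated limits without any assumption. The illustrative net excess of about 0.3 percentage points does rest on an assumed distribution.

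It would be wrong to infer that time in range, the >180 or >250 mg/dL endpoints, or the testing hierarchy are affected. Their definitions agree between the SAP body and Appendix A.

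**What to change.** - **Appendix A, DTSQc row:** add the baseline DTSQs score to the model, and replace the reference to change from baseline with the between-group LS mean difference at Week 12.
- **SAP 2.4.7:** describe baseline DTSQs as a continuous covariate in the DTSQc model, as is done for the other PRO models.
- **Appendix A, glucose band row:** change the limits to >180 to ≤250 mg/dL, for all-time and nocturnal summaries alike.

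The cost is a few words in the SAP, best changed before database lock. No new data, sample size or testing rule is involved.
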